10.7 Concomitant Medication

10.7.1 Recommended Concomitant Medication

10.7.1.1 Albumin

In keeping with standard medical practice and current guidelines, it is strongly recommended that albumin be administered to all subjects in both study arms. Albumin doses recommended by the IAC following the albumin fluid challenge are 20 g/day to 40 g/day as clinically indicated (Salerno et al, 2007; Angeli et al, 2015). It is recommended (if clinically appropriate) that the albumin dose is kept constant during the study drug administration period. For management of fluid overload, refer to Section 10.3.2.1.1.

10.7.1.2 Prohibited or Discouraged Concomitant Medications

The following medications are prohibited or strongly discouraged during treatment with study drug (Table 10–1).

Table 10–1 Prohibited/Discouraged Concomitant Medications

Prohibited Concomitant Medications

Midodrine and other vasopressive drugs including vasopressin, dopamine, dobutamine, norepinephrine. Prostaglandin analogs (eg, misoprostol).

NSAIDs (eg, ibuprofen, naproxen, diclofenac).

Octreotide.

Discouraged Concomitant Medications

Diuretics are strongly discouraged unless medically required for fluid overload; limited use of diuretics for the management of fluid overload as per standard of care may be employed and must be documented (Section 10.3.2.1.1).

10.8 Treatment Compliance

The treatment, dosage and time of administration for each dose of study drug will be documented. A monitor will review subject source documents and drug accountability records to assess treatment compliance on an ongoing basis during site visits.

10.9 Medical Hotline

The sponsor will maintain a 24-hour medical hotline for investigators to discuss subject issues including enrollment eligibility, unblinding, and retreatment. The hotline number will be provided in the study manual. All hotline communications will be documented.

11 Study Drug Material and Management

11.1 Study Drug and Reference Therapy

[figure not shown]
11.1.1 Terlipressin

The structure of terlipressin is presented in Figure 2. Single-use, sterile 6-mL vials containing 1 mg of lyophilized terlipressin acetate (equivalent to 0.85 mg terlipressin free base) with 10 mg mannitol as a bulking agent/stabilizer. Each vial will be reconstituted with 5 mL of sterile 0.9% sodium chloride solution.

The batch number will be documented in the trial master file.

Figure 2: Terlivaz® (Terlipressin for Injection)

Structure:

Molecular Formula: $C_{52} H_{74} N_{16} O_{15} S_2$

Molecular Weight: 1227.4 Daltons

Appearance: Homogenous lyophilized white to off-white solid

Solubility: Clear, colorless solution in saline

Terlipressin
Protocol MNK19013058
Incorporating Amendments 1, 2 and 3

Vials: Colorless glass vials containing 11 mg of a white to off-white

solid, 1 mg active ingredient and 10 mg mannitol.

The active ingredient, N-[N-(N-glycylglycyl) glycyl]-8-L-lysinevasopressin, is a synthetically manufactured hormonogen of 8-lysine vasopressin, composed of 12 amino acids and having the characteristic ring structure of a cyclic nonapeptide with a disulfide bridge between the 4th and the 9th amino acid. Three glycyl-amino acids are substituted at position 1 (cysteine) of 8-lysine-vasopressin. By this N-terminal extension of 8-lysine-vasopressin, the metabolic degradation rate of the active ingredient is significantly reduced, because the glycyl molecules inhibit rapid N-terminal enzymatic degradation.

11.1.2 Placebo

Matching placebo vials (containing 11 mg mannitol) are identical in appearance to terlipressin for injection vials. Each vial will be reconstituted with 5 mL of sterile 0.9% sodium chloride solution.

11.2 Packaging and Labeling

Single-use, sterile 6-mL vials of a lyophilized solid containing 1 mg of terlipressin acetate (equivalent to 0.85 mg terlipressin free base) with mannitol or matching placebo (mannitol only) will be provided to the sites. Study drug labels will comply with local regulatory requirements, including sponsor name and address, protocol number, kit number, storage conditions and US Investigational New Drug (IND) caution statement.

11.3 Study Drug Storage and Preparation

Study drug should be stored in a secure location at 2°C to 8°C until reconstitution and can be stored up to 48 hours at refrigerated storage conditions (2°C to 8°C) once reconstituted with sterile 0.9% NaCl solution.

Access will be strictly limited to the investigators and their designees.

11.3.1 Reconstitution

Each vial of study drug will be reconstituted with 5 mL of sterile 0.9% sodium chloride solution.

11.3.2 Administration

Reconstituted study drug should be administered via a slow bolus (IV push over 2 minutes). See Section 10.1 for details.

After study drug administration the line should be flushed with saline.

11.4 Study Drug Accountability

The investigator or designee must maintain an inventory record of study drug administered to assure the regulatory authorities and the sponsor that the investigational new drug will not be dispensed to any person who is not a subject under the terms and conditions set forth in this protocol. Neither the investigators nor any designees may provide study drug to any subject not formally enrolled in this protocol.

The study drug supplied for use in this study is to be prescribed only by the investigator or named sub-investigators and may not be used for any purpose other than that outlined in this protocol.

All unused investigational product will be handled as outlined in the pharmacy manual. Periodic review of drug accountability records will be conducted by investigational site monitors. Final review and reconciliation of the accountability records will be performed by the sponsor or designee.

12 Randomization, Breaking of Blinded Codes

12.1 Randomization and Blinding

12.1.1 Randomization

After the subject has signed the informed consent form (ICF), the investigator or qualified designee will complete the subject qualification form, along with the required supportive documentation (including SCr values during hospitalization and details of albumin fluid challenge administration and diuretic withdrawal), and forward to the sponsor for review and approval of subject enrollment.

Randomization will occur only after a diagnosis of HRS Type 1 is established, written informed consent has been obtained from the subject or representative, and subject eligibility is confirmed. Once a subject is randomized, the subject is considered a study participant.

Terlipressin
Protocol MNK19013058
Incorporating Amendments 1, 2 and 3

Even if study drug is not subsequently administered, the subject must be followed-up for mortality assessments.

A total of 300 subjects are planned to be randomized via an IXRS. Each successive subject will be assigned a unique identification number. Allocation will be made to 1 of 2 treatment groups, ie, terlipressin or placebo, in a 2:1 ratio. Both treatment groups will be studied concurrently. Randomization will be stratified by qualifying SCr (less than 3.4 mg/dL or at least 3.4 mg/dL) and pre-enrollment LVP (at least one single event of at least 4 L or less than 4 L within 3 to 14 days prior to randomization). Note, subjects with a LVP of at least 4 L are excluded if it occurs within 2 days prior to randomization (refer to Section 8.4).

12.1.2 Blinding of Study Drugs

The active and placebo vials will be labeled with single panel labels comprised of randomized identification numbers for each kit to maintain the blinding of the randomized treatments. Refer to the pharmacy manual for additional details.

12.1.3 Unblinding of Treatment Assignment

Unblinding of treatment assignment should be done only in the event that definite knowledge of the study drug is essential for the medical treatment of the subject. If possible, the investigator should contact the sponsor via the Medical Hotline prior to unblinding. In the event that unblinding of an individual subject is required, the investigator will be able to call into the IXRS system to unblind a subject.

The sponsor must be immediately informed of any unblinding and the site must document the date and reason for unblinding in writing, as well as the method used.

13 Assessments and Procedures

13.1 Schedule of Assessments and Procedures

Table 13–1 presents the schedule of assessments and procedures to be performed during the study.

Table 13–1 Schedule of Assessments

Study Assessment		Pre- Treatment Period			Follow-up Period (Days from 1st Dose) ^c											
	Screening	Baseline Assessment	Days 1	to 14 ^a	as a	pplic	able)				End of Treatment	10 Days After 2 nd SCR ≤ 1.5 mg/dL	Day 14 b or Discharge whichever occurs first			
	Period		1	2	3	4	5	6	7	8 to 14 ^a				30 days $\pm 10 d^{t}$	60 days ± 14 d	90 days ± 14 d
Diagnosis of HRS Type 1	X															
Informed consent	X															
Inclusion/exclusion criteria	X	X														
Verification of study qualification	X															
Demographics	X															
Height and body weight	X															
Pregnancy test d	X															
Prior medications	X	X														
Record all pre- enrollment paracentesis prior to randomization e,f	X	X														
Baseline SCr prior to randomization f	X	X ^g														
Randomization		X														
Medical history h	X	X				_								X		

Study Assessment		Pre- Treatment Period			Follow-up Period (Days from 1st Dose)											
	Screening	Baseline Assessment	Days 1 t	to 14 ^a	(as a	pplica	able)				End of Treatment	10 Days After 2 nd SCR ≤ 1.5 mg/dL	Day 14 b			
	Period		1	2	3	4	5	6	7	8 to 14 ^a			or Discharge whichever occurs first	30 days ± 10 d ^t	60 days ± 14 d	90 days ± 14 d
Physical examination (including weight and height)		x ⁱ	x ^u	x ^u	xu	xu	x^{u}	x^{u}	xu	x ^u				x^{i}		
12-lead ECG ^j		X														
Child-Pugh score		X														
Urine sample for biomarkers		Х														
Blood sample for biomarkers		Х														
Venous blood lactate		X														
Study drug administration as applicable			X	X	X	X	X	X	X	X						
Daily Assessments (1	regardless of	treatment status	s)													
Record albumin dose administered		X	X	X	X	X	X	X	X	X	X		X			
SCr & BUN ^m		X	X	X	X	X	X	X	X	X	X		X	χ^{m}		

Study Assessment	Screening Period	Pre- Treatment Period				Follow-up Period (Days from 1st Dose)										
		Baseline Assessment	Days 1 t	to 14 ^a	(as a	pplica	able)				End of Treatment	10 Days	Day 14 b			
			1	2	3	4	5	6	7	8 to 14 ^a		After 2 nd SCR ≤ 1.5 mg/dL	or Discharge whichever occurs first	30 days ± 10 d ^t	60 days ± 14 d	90 days ± 14 d
Confirmatory SCr at minimum of 2 hours after initial SCr of ≤ 1.5 mg/dL			Х	х	x	x	x	X	X	Х	Х		x ⁿ			
Site to confirm subject survival for verified reversal												Х				
Record open label vasopressor use ^p			X	X	x	x	x	X	X	X	X		X			
Assessments ONLY	On Treatmen	t During Days	1 to 14													
Vital signs ^q		X	X	X	X	X	X	X	X	X	X			X		
Encephalopathy score		X	X	Х	X	X	X	X	X	X						
Serum electrolytes		X	X	X	X	X	X	X	X	X	X					
ALT, AST, ALP, protein, albumin, bilirubin		X	X		X				X		X					
Serum glucose, calcium, magnesium		X	X		X				X		X					
INR		X	X		X				X		X					

	Screening Period	Pre- Treatment Period Baseline Assessment			Follow-up Period (Days from 1st Dose)											
			Days 1	to 14 ^a	as a	pplic	able)				End of Treatment	10 Days After 2 nd SCR ≤ 1.5 mg/dL	Day 14 b or Discharge whichever occurs first			
Study Assessment			1	2	3	4	5	6	7	8 to 14 ^a				30 days ± 10 d ^t	60 days ± 14 d	90 days ± 14 d
CBC and differential		X	X		X				X		X					
Concomitant medications r			X	X	х	Х	х	X	X	X				X		
Assessments Throug	hout Study										•			•		
Adverse events			Monitor and record throughout active study period to 7 days post-treatment for AEs, 30 days post- treatment for SAEs.										X			
HRS Type 1 recurrence assessment							Mon	itor ar	nd rec	ord through	hout active stu	dy period	and follow-up	р.		
Record events of RRT, TIPS, transplant, and mortality							Mon	itor ar	nd reco	ord througl	hout active stu	dy period	and follow-up).		

	Screening Period	Pre- Treatment Period		Active Study Period												d Dose) ^c
C4 d.v. A sees seement			Days 1 t	o 14 ^a	(as a	pplica	able)	T	•		End of Treatment	10 Days After 2 nd SCR≤ 1.5 mg/dL	Day 14 b or Discharge whichever occurs first			
Study Assessment		Baseline Assessment	1	2	3	4	5	6	7	8 to 14 ^a				30 days ± 10 d ^t	60 days ± 14 d	90 days ± 14 d
Record all paracentesis events				Record all paracentesis performed after study drug treatment discontinued to 30-day follow-up												

Abbreviations: ALP = alkaline phosphatase, ALT = alanine aminotransferase, AST = aspartate aminotransferase, BUN = blood urea nitrogen, CBC = complete blood count, d = day; ECG = electrocardiogram, HRS = hepatorenal syndrome, INR = international normalized ratio, LVP = large volume paracentesis, RRT = renal replacement therapy, SCr = serum creatinine, TIPS = transjugular intrahepatic portosystemic shunt.

Note, subjects with a LVP of at least 4 L are excluded if it occurs within 2 days prior to randomization (refer to Section 8.4).

The investigator must review any paracentesis in the pre-enrollment period and volume status after paracentesis must be considered carefully; as per standard of care, adequate replacement of fluid removed with albumin is required. A paracentesis is considered a LVP if at least 4 L of fluid is withdrawn in a given procedure (Choi et al, 2005; Kao et al, 1985; Ginès et al, 1987; Pinto et al, 1988; Tito et al, 1990).

No subjects should be randomized unless their SCr has been obtained within 8 hours prior to randomization and start of study drug. If there is a delay in subject randomization, then the qualifying/baseline SCr value must be redrawn so that the value is collected within 8 hours prior to randomization and start of study drug to verify that the subject still meets the inclusion criterion for baseline SCr.

^aSame procedures and assessments on Day 15 if response first occurs on Day 14.

^bDay 15 if response first occurs on Day 14.

^cFollow-up assessments must also be completed for subjects randomized but not treated with study drug. Study days will be counted from first day of study drug administration (or from randomization for those subjects who do not receive study drug).

^dFemale subjects of child-bearing potential must have a negative urine or serum pregnancy test within 14 days prior to the first dose of study treatment.

^eDate and volume of all pre-enrollment paracentesis will be recorded in the eCRF.

^fAll pre-enrollment paracentesis and baseline SCr to be recorded before randomization (and required for IXRS).

The qualifying SCr value (SCr value at least 48 hours after both diuretic withdrawal and the beginning of albumin fluid challenge) is considered the baseline SCr and must be drawn no more than 8 hours prior to start of study drug. The qualifying SCr value must be at least 2.25 mg/dL AND at least 80% of the diagnostic (pre-fluid challenge) SCr value.

hMedical history will include assessment of multi-organ dysfunction at baseline (refer to Section 13.3.5 and the Site/Investigator Study Manual for additional details).

A general physical assessment of the major body systems evaluating any new clinically significant abnormalities within the following: general appearance, skin, head/eyes/ears/nose/throat, neck, heart, lungs, abdomen, extremities, and neurological systems, the physical examination will also include weight and height.

^JA 12-lead ECG will be performed at baseline. Clinically relevant abnormalities found will be reported on the medical history page. The investigator may perform additional unscheduled examinations to manage or evaluate a suspected AE as clinically necessary.

^kBoth urine and blood samples for biomarker evaluation will be collected once at baseline; participation in this project will not affect participation in the main study.

Treatment should be continued until 24 hours after 2 consecutive SCr values no more than 1.5 mg/dL have been obtained, OR up to a maximum of 14 days (maximum of 15 days if SCr first reaches 1.5 mg/dL on Day 14, when the Day 14 assessments will be performed on Day 15). Window is (± 30 minutes).

mMust be performed at least once daily during active treatment AND until Day 14 (regardless of treatment status) or discharge, whichever occurs first. If SCr and/or BUN assessments are performed more than once daily as part of the subject's medical care, all values are to be recorded on the eCRF. At 30-day follow-up visit, collect SCr only (no BUN).

ⁿA blood sample for measurement of SCr must be drawn before discharge. The second verifying sample of SCr no more than 1.5 mg/dL must be taken at least 2 hours apart and must be consecutive.

^oIf a subject meets the primary end point (2 consecutive SCr values of no more than 1.5 mg/dL), the subject's survival and RRT status must be confirmed 10 days after the date of the second SCr. This follow up is required regardless of whether the subject remains hospitalized or has been discharged. If the subject has been discharged, follow-up may be by phone.

PRequired for evaluation of efficacy endpoints.

 $^{^{}q}$ Vital sign measurements include body temperature, respiratory rate, systolic and diastolic blood pressure, SpO₂ (pulse oximetric saturation), and heart rate. Time points for systolic and diastolic blood pressure and heart rate: predose and postdose at 5 (\pm 2) min and 2 (\pm 0.25) h for every dose. Time points for body temperature, respiratory rate, and pulse oximetric saturation (SpO₂): once daily.

^rConcomitant medications include IV solutions and blood products.

^SAll subjects will be required to come back for Day 30 (\pm 10) visit and will be contacted by phone for Day 60 (\pm 14), and Day 90 (\pm 14) follow up to assess survival, RRT, TIPS and liver transplant status. Study days will be counted from first day of study drug administration (or from randomization for those subjects who do not receive study drug). All information regarding RRT, TIPS and liver transplant must be collected.

For the Day 30 follow-up visit, all subjects are required to provide a blood sample for SCr. The site staff must also collect an updated medical history, vital signs, concomitant medications, SAE assessment, paracentesis events, RRT, and HRS recurrence.

^uThe investigator should perform daily abbreviated physical examinations through the end of treatment to evaluate suspected AEs.

13.2 Study Assessment Periods

13.2.1 Screening Period

The screening period occurs prior to enrollment and consists of establishing the diagnosis of HRS Type 1 as per guidelines and standard medical practice and confirming eligibility for study participation. The investigator or qualified designee will complete the subject qualification form along with the required supportive documentation (including SCr values during hospitalization and details of albumin fluid challenge administration and diuretic withdrawal) and forward to the sponsor for review and approval of subject enrollment. Written informed consent will be obtained by the investigator, sub-investigator, or qualified designee from the subject or legally authorized representative prior to the subject qualification form being completed.

Subjects screened but not enrolled in the study for any reason should be recorded on the screening log. These subjects are not considered study participants and no additional follow-up is required.

The investigator must review any paracentesis performed in the pre-enrollment period and volume status after paracentesis must be considered carefully; as per standard of care, adequate replacement of fluid removed with albumin is required.

13.2.2 Pre-Treatment Period

The pre-treatment period occurs prior to administration of study drug and includes performing baseline assessments and collection of prior medication information.

• The qualifying SCr value (SCr value at least 48 hours after both diuretic withdrawal and the beginning of albumin fluid challenge) is considered the baseline SCr and must be drawn no more than 8 hours prior to start of study drug. The qualifying SCr value must be at least 2.25 mg/dL AND at least 80% of the diagnostic (pre-fluid challenge) SCr value. No subjects should be randomized unless their SCr has been obtained within 8 hours prior to randomization and start of study drug. If there is a delay in subject randomization, then the qualifying/baseline SCr value must be redrawn so that the value is collected within 8 hours prior to randomization and start of study drug to verify that the subject still meets the inclusion criterion for baseline SCr. The qualifying serum creatinine for subjects on prior vasopressors will be taken after completion of vasopressor washout. Other baseline assessments must be performed no more than 24 hours prior to start of study drug.

13.2.3 Active Study Period (14 Days)

13.2.3.1 Dosing (Up to 14 Days)

The active study period extends from the initiation of study treatment through Day 14 (Day 15 as described in Section 10.4) or discharge from the hospital for any reason, whichever occurs first. Study drug will be administered as described in Section 10.3. Concomitant medications will be collected during this active study period.

See Table 13–1 for the schedule of assessments during the active study period.

13.2.3.2 End of Treatment, Discharge or Day 14

Treatment should be continued until 24 hours after 2 consecutive SCr values no more than 1.5 mg/dL have been obtained, OR up to a maximum of 14 days (maximum of 15 days if SCr first reaches 1.5 mg/dL on Day 14, when the Day 14 assessments will be performed on Day 15).

Following HRS reversal (SCr no more than 1.5 mg/dL), repeat values for SCr must be obtained a minimum of 2 hours after the first SCr value. Every effort must be made to collect these SCr values.

All information regarding paracentesis events, RRT, TIPS, liver transplant, or open-label vasopressor use must be collected.

The subject will be contacted to determine the status of survival without RRT at 10 days after the second SCr value no more than 1.5mg/dL is attained.

13.2.4 Follow-up Period

The follow-up period begins after the end of the study treatment and concludes 90 days following the start of treatment. Study days will be counted from first day of study drug administration (or from randomization for those subjects who do not receive study drug).

All subjects will have a follow up visit on Day 30 (±10 days) while Day 60 (± 14), and Day 90 (± 14) follow up can be done via telephone to assess survival, RRT, TIPS, and liver transplant status. Study days will be counted from first day of study drug administration (or from randomization for those subjects who do not receive study drug). In addition, during the Day 30 follow-up, a blood sample will be obtained to assess serum creatinine. A physical examination, updated medical history, vital signs, concomitant medications, and SAE assessments, paracentesis events, RRT, TIPS, and liver transplant status will also be collected.

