- Non-serious adverse events up to 7 days after end of treatment.
- Serious adverse events up to 30 days after end of treatment.
- General safety profile, including physical examinations, vital signs and laboratory tests.
- Mortality up to 90 days after the first dose of study drug.

7 Investigational Plan

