8.5 Subject Withdrawal Criteria

Subjects have the right to discontinue treatment and/or withdraw from the study at any time without prejudice. The investigator may discontinue any subject at any time for any reason. If study treatment or protocol-specified assessments are discontinued, the reason will be recorded and the sponsor should be notified promptly. If a subject withdraws from the study, the reason will be recorded on the eCRF. Reasons for terminating participation in the clinical study may include the following:

- Adverse event(s).
- Abnormal laboratory value(s).
- Abnormal test procedure result(s).
- Protocol-noncompliance.
- Withdrawal of consent.

Terlipressin
Protocol MNK19013058
Incorporating Amendments 1, 2 and 3

- Lost to follow-up.
- Administrative problems.

It is imperative to obtain complete follow-up data for all randomized subjects, whether or not they received their assigned study treatment, altered or discontinued study drug prematurely. Every attempt should be made to collect follow-up information, including required laboratory tests, serious adverse events (SAEs) and mortality assessments, except for those subjects who specifically withdraw consent for release of such information. Sites should contact subject/family member via telephone, mail or both to obtain this information. At least 3 documented attempts should be made by the site. Subjects withdrawn from treatment due to an adverse event should be followed until the event resolves, is no longer clinically significant, has stabilized, or is otherwise explained. Withdrawal of consent for follow-up should be accompanied by documentation of the reason for withdrawal. Withdrawal of consent for treatment should be distinguished from withdrawal of consent for follow-up contact and from withdrawal of consent for non-subject contact follow-up (eg, medical records checks). Sites should do the utmost to obtain the withdrawal of consent in writing and, if the subject or the subject's representative refuses or is physically unavailable, the site should document and sign the reason for the subject's failure to withdraw consent in writing.

9 Protocol Deviations

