13.4.4 Adverse Events

All adverse events will be assessed and recorded beginning with study drug administration until 7 days after discontinuation of study drug. Adverse events considered serious will be assessed and recorded until 30 days after discontinuation of study drug; excluding deaths, which will be collected up to 90 days after the first dose of study drug.

Those events that are serious in nature must be reported to the sponsor or its designee for safety reporting in an expedited manner (see Section 14 for definitions and reporting requirements).

The adverse event collection schedule for the proposed study is adopted from the previous clinical studies in the same patient population and for the same drug. The time frames for collecting various types of adverse events are defined to focus on the collection of safety information pertinent to the study subjects in the proposed study, as the target patient population has an extensive health background and existing medical conditions.

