15.1 Safety Variables

Safety variables will include the following:

- Adverse events.
- Serious adverse events, including deaths.
- Vital signs (body temperature, blood pressure, heart rate, respiratory rate, and SpO₂).
- MELD score.
- Encephalopathy score.
- Laboratory parameters other than SCr.

Adverse events will be collected from the start of study drug administration, during treatment and up to 7 days post end of treatment and at each evaluation. Adverse events considered serious will be collected up to 30 days after the end of treatment. Deaths up to 90 days will be reported as SAEs. Adverse events will be classified by Medical Dictionary for Drug Regulatory Activities (MedDRA) system organ class, preferred term, severity, and seriousness, as well as by the investigator's assessment of the relationship of the AE to the study drug.

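### The last survival contact may fall on Day 76, and no visible text requires a vital-status check on or after Day 90, so deaths on Days 77–90 could be missed

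*Combined protocol and SAP*

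**What the plan says.** **Contact schedule.** Section 13.2.4 states that the "Day 90 (± 14) follow up can be done via telephone to assess survival, RRT, TIPS, and liver transplant status". The Synopsis (Duration of Treatment), Section 7.1, and Table 13–1 with its footnote on follow-up contacts carry the same ± 14 days. The footnote gives the purpose as "follow up to assess survival, RRT, TIPS and liver transplant status".

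**Mortality horizon.** The safety assessments in Section 6.1.5 include "Mortality up to 90 days after the first dose of study drug". Section 13.4.4 ends collection of serious adverse events 30 days after study drug stops, "excluding deaths, which will be collected up to 90 days after the first dose of study drug"; Section 14.2 repeats this. Section 15.1 adds: "Deaths up to 90 days will be reported as SAEs".

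**Other text on follow-up.** Section 13.2.4 opens with: "The follow-up period begins after the end of the study treatment and concludes 90 days following the start of treatment". Table 13–1 has a row headed "Record events of RRT, TIPS, transplant, and mortality", to be completed through the active period and follow-up. Section 8.5 says: "Every attempt should be made to collect follow-up information, including required laboratory tests, serious adverse events (SAEs) and mortality assessments", and asks for at least three documented attempts.

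**The concern.** The collection duty runs to Day 90, but the last scheduled means of meeting it may be used two weeks earlier. A site that reaches a subject alive on Day 76 has made every contact the schedule asks for, and no later contact is scheduled. If the subject has been discharged and dies on Day 82, the site may never hear of it.

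At stake is the completeness of 90-day mortality, an outcome that readers of the safety results will look at closely in this population. The same window applies to RRT, TIPS and transplant status at the last contact. The Day 30 visit (± 10 days) has the same two-sided form, but the later contacts and the serious adverse event data partly cover that gap; nothing scheduled follows the Day 90 call.

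**Working it through.** **1. Window arithmetic (Section 13.2.4).**

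- Earliest final contact: 90 − 14 = Day 76. Latest: 90 + 14 = Day 104.
- Worst-case gap after the last scheduled contact: Days 77–90, which is 14 of 90 days (15.6%).
- A call on Day 85 leaves 5 days; a call on Days 90–104 leaves none.

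**2. Does another rule close the gap?**

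- Sections 13.4.4, 14.2 and 15.1 and the mortality row of Table 13–1 say what must be recorded and until when. They do not say how a site learns of a death after discharge.
- Routine collection of serious adverse events ends 30 days after study drug stops. With at most 15 days of initial treatment (Section 10.4), that is about Day 15 + 30 = 45, well before Day 76. A retreated subject may remain under observation for longer.
- The effort clause and the three attempts in Section 8.5 help when a subject cannot be reached. They do not ask for a second call to a subject who has been reached.

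**3. Size, model A.** The documents give no mortality rate, so all inputs here are assumptions, apart from the planned 300 subjects (Section 8.2). Let *m* be 90-day mortality and *k* the Weibull shape (*k* = 1 is a constant hazard, *k* < 1 a falling one):

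S(t) = exp{ln(1 − m) × (t/90)^k}

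Deaths on Days 77–90 per 300 = 300 × [S(76) − S(90)], where S(90) = 1 − m. This is the number missed if every call falls on Day 76 and nothing else reveals the death. For calls spread evenly over the 29 days from 76 to 104, average S(d) − S(90) over those days, with zero from Day 90 on.

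| m | k | S(76) | S(76) − S(90) | Missed per 300, all calls on Day 76 | Missed per 300, calls spread evenly |
|---|---|---|---|---|---|
| 40% | 0.5 | 0.6254 | 0.0254 | 7.6 | 1.93 |
| 40% | 1.0 | 0.6496 | 0.0496 | 14.9 | 3.80 |
| 60% | 0.5 | 0.4308 | 0.0308 | 9.3 | 2.33 |
| 60% | 1.0 | 0.4613 | 0.0613 | 18.4 | 4.65 |

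These corners give about 8–18 deaths in the extreme case and about 2–5 with even spread. The values at m = 50% lie between.

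**4. Size, model B (lower late risk).** Let *a* be the share alive at Day 76 (assumed 40–70%) and *r* the 30-day risk of death among those survivors (assumed 2–10%):

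Missed = 300 × a × [1 − (1 − r)^(14/30)]

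- a = 0.4, r = 0.02: 300 × 0.4 × 0.00938 = 1.1 deaths (0.4 percentage points).
- a = 0.7, r = 0.10: 300 × 0.7 × 0.04798 = 10.1 deaths (3.4 percentage points).

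This also assumes that every call falls on Day 76 and that there is no other source of information.

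**5. After the fix.** If the last contact cannot precede Day 90, the worst-case gap falls from 14 days to 0. No sample size, power or alpha figure changes.

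**The case against.** The strongest reply is that the protocol does ask for these deaths. Sections 13.4.4 and 14.2 require deaths to be collected to Day 90, Section 15.1 has them reported as serious adverse events, and Section 14.3.1 requires a report within 24 hours of the investigator becoming aware. Follow-up ends at Day 90, not at the date of the call, and mortality is recorded throughout it. None of these duties depends on the scheduled contact.

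This stands, and it limits the point. A reader might infer from the window that deaths on Days 77–90 fall outside data collection, or that a subject reached alive on Day 76 has finished follow-up. The documents support neither reading. What remains is that the duty has no scheduled means of fulfilment after an early call.

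A reader might also infer that reported 90-day mortality will be too low, or distorted between arms. Neither can be asserted. The visible text does not say that subjects last seen alive before Day 90 count as survivors. Section numbering jumps from 6.1.2 to 6.1.5 and from 15.3.6.2 to 15.3.6.4, so a survival analysis with a censoring rule may be in blacked-out text. Censoring at the date last known alive would mainly cost precision, though it would not recover the unobserved deaths. A difference between arms would need call timing or late mortality to differ by arm; the trial is double-blind with one schedule for both, and nothing in the documents shows such a difference.

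Finally, the sizes above are upper-end illustrations, because they set all other ascertainment to zero.

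**Conclusion.** The point holds as a gap in ascertainment. The window permits a last scheduled contact up to 14 days before the mortality horizon, and no visible text requires a later check, so Day 90 vital status can be unknown for a subject whose site kept to the schedule.

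Under the stated assumptions the likely size is small: about 2–5 deaths of 300 with evenly spread calls. The 8–18 of model A and the 1–10 of model B both need every call on the first permitted day. Deaths learned of by other routes reduce all these figures.

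Mortality is outside the visible primary endpoint and the four secondary endpoints, so the confirmatory tests are untouched. The change should be made because it protects an important safety outcome at almost no cost; the validity of the trial does not depend on it.

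**What to change.** Open the last window at Day 90, that is Day 90 (+14). Alternatively, keep the present window and require vital status, RRT, TIPS and transplant status to be confirmed as of Day 90 or later whenever the call was made earlier. Make the same change in the Synopsis, Section 7.1, Table 13–1 with its footnote, and Section 13.2.4.

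If the analysis plan does not already do so, it should also state how a subject last known alive before Day 90 is handled in the 90-day mortality summary.

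The cost is protocol wording, plus some telephone calls made up to two weeks later or repeated. No visit is added and the sample size does not change.
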